- Cognitive dysfunction which limits the ability of the participant to adequately understand procedures and risks.
- Prisoners

- Pregnant Women

Special populations:

- Adults unable to consent: excluded from study
- Individuals -who are not yet adults: individuals who are less than 18 years old will be excluded from the study
- Pregnant women: Women who are known to be pregnant will not be recruited into the study. A pregnancy test will be administered to females prior to enrollment in TENS (or sham) treatment. Women who become pregnant before or during the 8-week TENS treatment period will be discontinued from the study. Women who become pregnant after the 8-week TENS treatment portion of the study will continue to be enrolled, and followed according to protocol guidelines (no information will be collected specifically on the pregnancy or fetus).
- Prisoners: excluded from study
- Neonates: not applicable

5) Number of Subjects*

This is a single-site study and 98 potential participants with newly-acquired spinal cord injuries will be enrolled. See section 22, for more information.

6) Study-Wide Recruitment Methods*

This is not a multi-center study. See section 21.

7) Study Timelines*

It is anticipated that subjects will be enrolled in the study for 12 months (see **Figure 5**, in section 10, below, for procedures timeline).

It is anticipated that enrollment of subjects will occur between November 1, 2016 and January 1, 2022. This enrollment end date is 12-months prior to the end of the funding cycle for this grant, which will allow for complete follow-up of all subjects before study termination.

The estimated date for the investigators to complete this study is October, 2022.

8) Study Endpoints*

The primary study endpoints/outcomes are: 1.) the percentage of subjects who develop chronic neuropathic pain at the 12-month post-spinal cord injury time point (as defined by a score of ≥ 2 on the Spinal Cord Injury Pain Inventory (SCIPI), a self-report scale of symptoms); and 2.) the severity of chronic neuropathic pain (as measured by a self-report rating of neuropathic pain symptoms) measured at the 12-month post-spinal cord injury time point. The secondary study endpoints/outcomes include other aspects of pain symptoms and physical and emotional function. All outcomes and other variables are listed in Table 2 and described in detail below, within the “Procedures Involved” section.

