Assessments of primary and secondary outcome measures will occur at the time points

diagramed in Figure 5. Details regarding the specific assessment tools and measures to be used are described below and listed in **Table 2**. The primary outcome variables for Aim 1 (Spinal Cord Injury Pain Instrument (SCIPI)⁸⁰ score of ≥ 2 , and Neuropathic Pain Symptom Inventory score⁸⁹) will be collected during each scheduled assessment (full and abbreviated assessments), with additional outcome measures recorded less frequently (during full assessment sessions only: 4 times during the study).

Randomization and blinding procedures:

A blocked randomization procedure will be used, so that for each eight patients enrolled, four will be allocated to TENS and four to Sham TENS. A computer-generated random assignment sequence will only be accessible to the study staff member responsible for delivering TENS treatments. The PI of the study, the researchers evaluating pain diagnoses, and the research subject will not be informed of the treatment allocation assigned. All subjects will be told that they may or may not feel the stimulation from the TENS unit during treatment sessions due to the parameters of the study. The stimulation parameters of the TENS unit will not be visible to the subject, so that subjects will not obviously know to which study group they were randomized.

Treatment procedures:

(a) *TENS device*: The TENS 7000 Dual Channel battery-powered digital stimulator (Roscoe Medical, Ohio, USA) will be used. This device provides for adjustable frequency/pulse rate, pulse width, and amplitude, as well as recording of session data (settings and duration of treatment session). The TENS 7000 device has two channels. Each channel will be connected to two self-stick square electrodes (thus, a total of 4 electrode pads will be used) with dimensions of 2 inches by 2 inches. New electrode pads will be used for each treatment session.

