Based on a total sample size of 98 subjects, and an estimated 15% drop-out rate, we expect that approximately 82 subjects will complete the study (i.e., 41 subjects per treatment arm). Based on previous work,^{21, 59} we project that 60% of subjects in the Sham TENS (control) group will have at- or below-level neuropathic pain at the 12 month follow-up time point. Thus, with 41 subjects in each group, $\alpha = 0.05$, power of at least 80%, and an analysis based on a two-sided Z-test (for group difference in proportion of subjects with neuropathic pain) for *Hypothesis 1a*, we will be able to detect at least a 50% reduction in the rate of subjects with chronic neuropathic pain in the TENS treatment group compared to the Sham group at 12 months post-SCI (i.e., Sham TENS = 60% with neuropathic pain; Treatment TENS = 30% neuropathic pain).

For t-test analyses assessing differences between groups (Sham vs. Treatment) using continuous variables (e.g., NRS, NPSI), 41 subjects in each group will allow for detection of a medium-to-large effect size (i.e., Cohen's $d = 0.6$) with α set at 0.05 and power of 0.80. Paired correlations will also be used for additional analyses (*Aim 2*). For correlations within group ($n = 41$), with power set at 0.80 and $\alpha = 0.05$, we will be able to detect a medium-to-large effect size (i.e., Cohen's $f^2 = 0.20$), and we will be able to detect a small-to-medium effect size for across-group analyses ($n = 82$; Cohen's $f^2 = 0.10$).

Data analysis plan:

Descriptive evaluations of the data will be performed for all variables to check the integrity of the data and to verify the underlying assumptions of the statistical tests that are planned. If necessary, and as appropriate, data will be transformed prior to any parametric analyses, or non-parametric techniques will be used with untransformed data. Statistical analyses will use two-tailed tests and an a-priori α of 0.05.

In addition to direct tests of hypotheses (described in detail below), descriptive analyses and graphical representations (e.g., spaghetti plots) of data will be used to describe longitudinal

characteristics of clinical pain, somatosensory function, and other physical and psychological outcomes across the 12-month timeline of study participation.

Hypothesis 1a:

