The PI will assign access to rooms, filing cabinets, and electronic files as necessary for completion of the study.

As this is a single site study, all data will remain on the University of Miami medical school campus, with access under the control of the PI.

12) Provisions to Monitor the Data to Ensure the Safety of Subjects*

Safety endpoints include frequency and severity of adverse events and increased likelihood of developing chronic pain due to TENS treatment. It is anticipated that only infrequent and mild adverse events (e.g., temporary skin irritation from surface electrode adhesive, brief mild pain during initial adjustment of TENS stimulation amplitude) will occur. These events will be handled on an individual basis and may be cause for the PI to discontinue participation of a subject who may be especially sensitive to the study treatment. If these mild adverse events are recorded at higher than expected frequency (i.e., greater than 10% of treatment sessions) or if an unexpected or moderate-severe adverse event occurs, the PI will re-evaluate the treatment parameters and adjust accordingly. All events will be reported to the IRB according to regulations.

Preliminary analyses will be performed after each group of 20 subjects completes the study to determine the efficacy of the treatment by comparing the primary endpoints between the two study groups (TENS and sham TENS). More frequent analyses will be performed if warranted. If these preliminary analyses at any point provide overwhelming support that the experimental intervention (TENS) reduces the development of chronic neuropathic pain or has a substantial clinically meaningful reduction in the severity of chronic neuropathic pain present, then the PI will pursue a change in protocol to provide the active TENS treatment to all available participants. Conversely, if the preliminary analyses reveal that the active TENS treatment puts patients at higher risk for pain or other undesirable outcomes, the PI will seek to terminate the intervention, but continue follow-up on enrolled participants.

13) Withdrawal of Subjects*

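### Severity is a primary endpoint in sections 8 and 9 but secondary in section 11: if either endpoint can succeed at 0.05, two-sided familywise error is about 8–10%; the unnumbered interim trigger in section 12 adds little if read strictly

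*Combined protocol and SAP*

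**What the plan says.** **Endpoint status.** Section 8 lists two primary endpoints at 12 months. The first is the percentage with chronic neuropathic pain (SCIPI of 2 or more). The second is "2.) the severity of chronic neuropathic pain (as measured by a self-report rating of neuropathic pain symptoms"). Section 9 (Overview) agrees: "The primary outcome variables for Aim 1 (Spinal Cord Injury Pain Instrument" at its cut-off, and the NPSI score, are named together. Later in section 9, the text on pain classification calls that assessment the primary outcome measure for Aim 1.

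Section 11 differs. Its power paragraph rests on "an analysis based on a two-sided Z-test (for group difference in proportion of subjects with neuropathic pain"), and Hypothesis 1a names that test as the primary statistical analysis. Severity by NRS and NPSI comes under secondary outcomes, with a remark that it will matter particularly if prevalence shows no difference.

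**Error rate.** The only statement is "Statistical analyses will use two-tailed tests and an a-priori" alpha of 0.05. No rule covers multiple endpoints or looks.

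**Interim looks.** Section 12 says that interim comparisons by arm "will be performed after each group of 20 subjects completes the study to determine the efficacy of the treatment by comparing the primary endpoints", and adds "More frequent analyses will be performed if warranted". The benefit trigger is "overwhelming support that the experimental intervention (TENS) reduces the development of chronic neuropathic pain or has a substantial clinically meaningful reduction in the severity" of existing pain. If it is met, the investigator "will pursue a change in protocol to provide the active TENS treatment to all available participants". The same analyses serve to detect harm.

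**The concern.** A reader cannot tell what makes this trial positive. Sections 8 and 9 allow a claim on severity alone; section 11 does not list severity as primary, yet stresses it in the one situation where a fallback claim is tempting. If both routes stay open at 0.05 each, the error rate is no longer 5%.

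Section 12 compounds this. It refers to primary endpoints in the plural, so both would be compared by arm at 20, 40, 60 and 80 completers, before their ranking is settled. The trigger has no number, and the plan does not say whether meeting it counts as a trial result or only prompts a proposed amendment.

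**Working it through.** **Inputs.** From section 11: 98 enrolled, 15% drop-out, 41 completers per arm, 60% v 30%, two-sided 0.05. From section 12: looks at 20, 40, 60 and 80 completers. The correlation between the two test statistics is not in the documents, so a range is shown.

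**1. The plan's own power.** 98 × 0.85 = 83.3, consistent with about 82 completers. With pooled rate 0.45:
- null SE = √(2 × 0.45 × 0.55 / 41) = 0.1099
- alternative SE = √((0.24 + 0.21) / 41) = 0.1048
- power = Φ((0.30 − 1.96 × 0.1099) / 0.1048) = Φ(0.81) = 79.0%

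Exact binomial calculation for the same pooled z test gives 81.25% power and a size of 5.5% at a 60% rate. The stated 80% stands.

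**2. Two endpoints, either may succeed at 0.05, final analysis only.** Two-sided error = 1 − P(|Z1| ≤ 1.96 and |Z2| ≤ 1.96). Benefit-direction error = 1 − P(Z1 ≤ 1.96 and Z2 ≤ 1.96). At correlation 0 the first is 1 − 0.95² = 9.75%.

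| Correlation | Two-sided | Benefit direction |
|---|---|---|
| 0 | 9.75% | 4.9% |
| 0.5 | 9.1% | 4.5% |
| 0.7 | 8.35% | 4.2% |
| 0.75 | 8.1% | 4.05% |
| 0.8 | 7.8% | 3.9% |
| 0.9 | 7.0% | 3.5% |

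A single test gives 5% and 2.5%. Patient-level simulation with 60% positive in both arms, a z test for SCIPI and a t test for NPSI gives 8.1–10.1% two-sided at simulated correlations of 0.79 down to 0.23. The NPSI distributions are assumed.

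**3. Interim looks, SCIPI alone.** Null simulation, 1,000,000 runs, independent increments, looks at 20/40/60/80 and a final two-sided 0.05 test at 82. Every interim crossing is counted as a positive result, which is an assumption.

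| Interim threshold | Two-sided | Benefit direction |
|---|---|---|
| p<0.001 | 5.1% | 2.6% |
| p<0.005 | 5.5% | 2.8% |
| p<0.01 | 6.2% | 3.1% |
| p<0.02 | 7.7% | 3.9% |
| p<0.05 | 13.1% | 6.5% |

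**4. Both gaps together.** Either endpoint at every look and at the end, patient-level simulation, two-sided: 8.3–10.3% with interim p<0.001, 10.4–12.5% with p<0.01, and 20–24% with p<0.05. Under the strict threshold nearly all the excess comes from step 2.

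**5. Which looks remain.** Section 7 plans enrolment from 1 November 2016 to 1 January 2022, which is 62 months. This version is dated 18 July 2022, about 68.5 months after the start. Enrolment within four months of injury puts the 12-month visit 8–12 months after enrolment. With even accrual, completers by the version date are 82 × (68.5 − 8)/62 = 80.0, 82 × (68.5 − 10)/62 = 77.4, or 82 × (68.5 − 12)/62 = 74.7. On planned dates the looks at 20, 40 and 60 are past, and the look at 80 is at or just after this version. Actual accrual is not in the documents.

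**The case against.** The strongest reply is that section 11 is the analysis plan. It names one primary test, sizes the trial on it and lists severity as secondary. Emphasis on severity when prevalence fails is not permission to call the trial positive. On that reading the error is that of the z test alone. This is a reasonable account of intent, and it is why the remedy follows section 11. But nothing says section 11 overrides sections 8 and 9, and section 12 itself uses the plural. Reading sections 8 and 9 as requiring both endpoints to succeed would also hold the error at or below 5%, but no such rule is written.

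On the looks, the reply largely stands. The wording for prevalence points to a strict threshold, and its stated consequence is a proposed protocol change, not a rejection. A reader might infer from section 12 that the looks alone inflate the error to 13% or more. The documents do not support that: it needs p<0.05 at every look and every crossing counted as a result, and neither is stated. Nor do they show that any look led to a change, or that sham subjects received active TENS before their 12-month endpoint.

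A reader might also take 8–10% as the chance of a false claim of benefit. It is a two-sided rate that includes findings of harm.

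**Conclusion.** The plan contradicts itself on what is primary, and following sections 8 and 9 as written gives the wrong error rate. Two-sided familywise error is about 8–10% for correlations from 0 to about 0.75 and 7–8% for 0.8–0.9, against the stated 5%. In the benefit direction it is 3.5–5% against 2.5%. This assumes that either endpoint may succeed alone at 0.05, with no interim action.

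The missing interim number is a lesser gap. It adds almost nothing at p<0.001, but without a stated threshold nobody can confirm how past looks were judged. The documents do not support saying that the trial's error is certainly inflated; they leave it undefined. It should be fixed before the final analysis, because a hierarchy set after the results are known would carry little weight.

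**What to change.** 1. **Reconcile sections 8 and 9 with section 11.** Make the single primary endpoint the 12-month proportion positive as Hypothesis 1a defines it, tested by the two-proportion z test at two-sided 0.05. That definition includes pain location and a separate rule, a rating of at least 4 out of 10, for subjects with early symptoms. Section 8 gives only the SCIPI cut-off, so the two definitions must be reconciled as well. Make 12-month NPSI a key secondary, tested confirmatorily only if the primary is significant.
2. **Report the looks already taken:** number, dates, content, and any action that followed.
3. **State in section 12** that any remaining efficacy look, scheduled or extra, can support a benefit claim only at a strict stated boundary, for example two-sided p<0.001 for either endpoint, with 0.05 kept for the final test. Keep every scheduled look, including the one at 80, because the same analyses serve harm monitoring.

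**Cost.** Wording in sections 8, 9, 11 and 12 and a short record of past looks; no new subjects or visits. The real price is that NPSI cannot be confirmatory if prevalence fails. Splitting alpha at 0.025 each would avoid that, but would cut exact power for the proportion from 81% to 69%. On planned dates the boundary covers few or no remaining looks, so the hierarchy and the disclosure are the main gain. If accrual ran late, the boundary does more.
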